2.4.3 Follow-up procedures

Post-surgical MEG testing:

We will ask the subject to come back for up to 3 MEG sessions within 6 months after completion of the BMI training. The follow-up MEG sessions are optional

visits for the subjects. If the subject is interested in participating, we will plan to schedule the visits at 2 weeks, 6 weeks, and 3 months after the explantation surgery. The same tasks that were completed during the pre-surgical MEG session will be repeated. In addition to measuring changes in single unit activity over the duration of the study, the MEG studies will allow us to determine if plasticity was induced due to BMI training in terms of volitional modulation of motor cortex activity. These visits are expected to last up to 2 hours each.

Clinical follow-up:

Follow-up visits will be scheduled in order to ensure that the bone flap and Patient Pedestal sites are healing properly. These visits will be scheduled at the discretion of the study neurosurgeon and the subject. We expect that each subject will have two follow-up visits with the study neurosurgeon and their clinical team at 1 and 4 weeks (+/- 3 days) after explantation. Depending on the healing process of the implantation site and percutaneous port, additional imaging studies (x-ray, CT scan, or MRI) may be performed although this is unlikely.

Post-explant counseling:

Subjects will be scheduled for an appointment with a licensed rehabilitation psychologist to assure that they have an opportunity to discuss any concerns they may have post explantation.

2.4.4 Study compliance and withdrawal:

The subject will be under medical supervision for the duration of this study. Their health will be the top priority and participation will be discontinued if surgical intervention is required. The study neurosurgeon and PI will be primarily responsible for evaluating the subject's condition. Complications that could result in removal from the study (and having the NeuroPort Array removed) include:

- Treatment resistant (serious) infection at the implantation site or Patient pedestal
- Array technical malfunction resulting in an inability to collect data that is useful for brain-control tasks
- Serious medical complications that compromise the subject's safety or health

If the participant is non-compliant (e.g., unwilling to participate in BMI training sessions) they may be withdrawn from the study. The NeuroPort Arrays will be explanted and they will be strongly encouraged to attend the follow-up monitoring visit with the study neurosurgeon.

Prior to implantation of the NeuroPort Array, the principal investigator may withdraw the participant if they do not demonstrate an understanding of the study or a willingness to participate. Participants can withdraw from the study at any time. The NeuroPort Arrays will be explanted and they will be strongly encouraged to attend the follow-up monitoring visits with the study neurosurgeon.

We will also ask for guidance from the DSMB if the research team and participant disagree on the decision to explant the NeuroPort Arrays (i.e., if the research team wishes to explant the arrays, but the participant does not).

2.4.5 Schedule of activities (Study Table)

Table 1 summarizes the study schedule.

Table 1: Study Schedule

Study Activities	Screening	Baseline/ Pre-operative Evaluation	Implant	Pre-Discharge	Discharge	Week 1	Week 2	Week 3	Week 4	Month 2-12	Explant/ End of Study
Screening Interview	X										
Informed Consent, Eligibility Assessments	X										
Neuropsychological and Psychosocial Examination (WTAR & BSI-18)	X										
Pre-surgical fMRI Screening	X										
Demographic and Medical History Questionnaire		X									
Pre-surgical Magnetoencephalography (MEG) Testing		X									
Pre-surgical BMI Training		X									
Pre-surgical Structural MRI		X									
Pre-operative Labs and Screening		X									
Implantation of Two NeuroPort Arrays			X								
Post Anesthesia Care Unit (PACU) Stay				X							
Neurosurgical Intensive Care Unit (ICU) Stay				X							
Rehabilitation Stay at UPMC Institute for Rehabilitation and Research				X							
Head X-ray and CT				X							
Ongoing psychological evaluations										X	X
Neurological and Musculoskeletal Exam; Wound Check by Clinical Investigator					X					X	X
BMI Training/Testing; Wound Check/Temperature Monitoring by Study Team*						X	X	X	X	X	
Pedestal Cleaning (at least weekly)						X	X	X	X	X	
Daily Temperature Monitoring/Wound Check by Primary Caregiver						X	X	X	X	X	
Explantation of NeuroPort Arrays											X
Post Anesthesia Care Unit (PACU) Stay											X
Neurosurgical Intensive Care Unit (ICU) Stay											X
Rehabilitation Stay at UPMC Institute for Rehabilitation and Research											X

Follow-up Clinical Visits with Neurosurgeon (1 & 4 weeks post-explant) and rehabilitation psychologist												X
Follow-up MEG Testing (2 weeks, 6 weeks, and 3 months post-explant)												X
Adverse Event Assessment	X	X	X	X	X	X	X	X	X	X	X	X

* BMI training may begin immediately after discharge or later as determined by the participant and study team; A wound check will be performed by a study team member weekly after discharge even if BMI training has not begun; BMI training will be conducted at least once per week for the duration of implantation either at the University of Pittsburgh, the University of Pittsburgh Medical Center (UPMC), or in the participant's home; Neural and behavioral data will be recorded during the BMI training/testing sessions in order to address the study specific aims.

2.5 Study outcome evaluations

2.5.1 Study endpoints

The NeuroPort Arrays will be removed 1 year (+/- 30 days) after implantation. A participant will be considered a success for safety if the device is not explanted for safety reasons during the 12-month post-implant evaluation. If the subject experiences treatment resistant (serious) adverse events, he or she will be withdrawn and the arrays will be explanted early (See Section E 2.4.4). The study may also end early if the subject is non-compliant (See Section E 2.4.4).

We believe it is possible that a participant will not want the array removed. If the participant wants the NeuroPort Arrays to stay in, the study PI and neurosurgeon will assess whether this is acceptable. This decision will be based on whether or not the participant is at increased risk by leaving the arrays in and whether the device is still measuring neural activity that is sufficient for brain control. We will consult our DSMB if conflicts arise. One participant in the BrainGate trial has had a NeuroPort Array implanted for more than 1000 days without adverse event [9]. If the NeuroPort Arrays remain implanted for more than 1 year, we will continue to perform clinical follow-up as described in the current protocol. We may also continue brain-machine interface testing although the frequency of the training sessions may be reduced. We will remove the NeuroPort Arrays at anytime as directed by the participant, or as dictated by their clinical condition.

If the participant wishes to leave the NeuroPort Array implanted, but the study PI and neurosurgeon do not feel that it is in their best interest, the participant will be counseled that they should have the NeuroPort Array removed and that not doing so could result in clinically significant adverse events. They will also be informed that brain-machine interface training will not continue. The consent form includes a statement that participants will be financially liable for any medical care resulting from complications of not having the device removed upon instruction of the study PI. We will however allow participants to have the device removed at anytime and the explantation costs would be covered by this study.

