Specific Aim 3: Source localization (combining the MEG and structural MRI data) will be used to identify the anatomical foci of cortical activation controlling imagined and/or attempted movement. The coordinates (x,y,z) of the center of activation can be computed with fMRI or MEG relative to the head coordinate system defined using bony landmarks. The location and area of cortical activation measured by fMRI and MEG during imagined and/or attempted movement will be compared for each subject. A paired t-test will be used to compare location and area of cortical activation measured by the two imaging techniques using data from all participants, although the power of this test may be limited by sample size. Qualitative comparisons will be informative and we expect agreement between the two imaging techniques in terms of localizing the area for array implantation. MEG

potentially offers additional information due to higher temporal resolution.

Specific Aim 3a: Cortical modulation will be calculated as the power of the 4-40 Hz frequency band of MEG data that is recorded during imagined and/or attempted movement. Specific Aim 3a will be evaluated by applying repeated measures ANOVA to test for differences in modulation (magnitude and total area) during imagined and/or attempted movement during the pre-surgical procedures and the follow-up sessions.

The study will be considered a success if the device is not explanted for safety reasons during the 12-month post-implant evaluation. Further participants should demonstrate successful control of a high degree of freedom assistive technology in order to safely perform a task that replicates normal activities of daily living, such as grasping a cup with a robotic manipulator. This study is not being proposed to support marketing applications (510(k) or PMA) for the NeuroPort Arrays. Instead, the goal is to demonstrate that three-dimensional microelectrode arrays provide a safe way to record sufficient neural information for controlling complex assistive devices that will increase the independence of individuals with disabilities.

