3.3.3 Inclusion criteria

- 1) Participant in PRO10080021 study (IDE G100298) who is at least 6 months post-implant
- 2) Have no unresolved significant adverse events during participation in PRO10080021
- 3) Have demonstrated at least 4-dimensional control of a virtual or real robotic arm during participation in PRO10080021
- 4) Have a stable psychosocial support and caregivers who are able to perform the necessary daily care of the participant's skin and pedestal site; This requires that the subject identify a caregiver and a back up who have been in place for greater than 6 months and are able to provide needed physical and psychosocial support. This will be assessed by the study PI and neurosurgeon.
- 5) Age 18-70 years old at the time of consent and planned explant
- 6) Have a life expectancy greater than 12 months as assessed by the study principal investigator and neurosurgeon sub-investigator
- 7) Live within 1 hour of the University of Pittsburgh, or be willing to travel there, once per week for BMI testing
- 8) Interested in having the NeuroPort arrays remain in place for 6 months to 4 years beyond the 1 year implantation that is part of PRO10080021. Participants can

decide to extend the implantation for any duration between 6 months and 4 years. This can be decided at any point during the study.

- 9) Participation is not expected to have an adverse effect on mental well-being as judged by the rehabilitation psychologist
- 10) Documentation of informed consent is obtained from the participant or their legal representative

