The study neurosurgeon may order a head x-ray or CT if there is a change in the patient's neurological examination or the patient experiences severe headaches, nausea, and/or abnormal behavior. These procedures will enable our neurosurgeon and their clinical team to identify infection, bleeding, edema, or neurological dysfunctions as early as possible and treat them properly. These imaging procedures will take place in UPMC facilities.

Removal of the electrodes:

Subjects will undergo a second surgery at UPMC Presbyterian Hospital approximately 5 years after implantation of the NeuroPort Arrays. It is possible that the NeuroPort Arrays may be explanted earlier due to technical problems, clinical complications, investigator-initiated withdrawal, or subject-initiated withdrawal. The participant will go through standard preoperative screening procedures which may include a blood draw. Explantation procedures are the same as described in Section 2.4.2.

Post-operative care:

Post-operative care will depend on the participant's condition. The participant will remain in the post anesthesia care unit (PACU) for approximately 3 hours after surgery. They will be transferred to the neurosurgical intensive care unit (ICU) for approximately 24 hours before transitioning to the neurosurgical medical surgery recovery unit where they will stay for 1-2 days. The PACU, ICU, and medical surgery recovery unit are all located at UPMC Presbyterian Hospital. Post-operative imaging may be requested by the study neurosurgeon depending on the

participant's condition. The participants will then stay at the UPMC Rehabilitation Institute for up to 3 days for post-operative rehabilitation. The rehabilitation stay serves primarily to ensure that the participant is ready to resume normal daily activities while medical staff can monitor wound healing. The study neurosurgeon, PI and rehabilitation team will determine when the participant will be discharged and sent home.

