3.5 Study outcome evaluations

3.5.1 Study endpoints

The NeuroPort Arrays will be removed up to 5 years after implantation. A participant will be considered a success for safety if the device is not explanted for safety reasons during the 5 year post-implant evaluation. If the subject experiences treatment resistant (serious) adverse events, he or she will be withdrawn and the arrays will be explanted early (See Section E 3.4.4). The study may also end early if the subject is non-compliant (See Section E 3.4.4).

If the participant wishes to leave the NeuroPort Array implanted after 5 years, the participant will be counseled that they should have the NeuroPort Array removed and that not doing so could result in clinically significant adverse events. They will also be informed that brain-machine interface training will not continue. The consent form includes a statement that participants will be financially liable for any medical care resulting from complications of not having the device removed upon instruction of the study PI. We will however allow participants to have the device removed at anytime and the explantation costs would be covered by this study.

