Specific Aim 3: Source localization (combining the MEG and structural MRI data) will be used to identify the anatomical foci of cortical activation controlling imagined and/or attempted movement. The coordinates (x,y,z) of the center of activation can be computed with fMRI or MEG relative to the head coordinate system defined using bony landmarks. The location and area of cortical activation measured by fMRI and MEG during imagined and/or attempted movement will be compared for each subject. A paired t-test will be used to compare location and area of cortical activation measured by the two imaging techniques using data from all participants, although the power of this test may be limited by sample size. Qualitative comparisons will be informative and we expect agreement between the two imaging techniques in terms of localizing the area for array implantation. MEG potentially offers additional information due to higher temporal resolution.

Specific Aim 3a: Cortical modulation will be calculated as the power of the 4-40 Hz frequency band of MEG data that is recorded during imagined and/or attempted movement. Specific Aim 3a will be evaluated by applying repeated measures ANOVA to test for differences in modulation (magnitude and total area) during imagined and/or attempted movement during the pre-surgical procedures and the follow-up sessions.

Specific Aim 4: Sleep quality measures will be correlated to BMI performance on the following day while controlling for differences in task difficulty. Linear regression will be used to determine the most predictive sleep quality metrics.

The study will be considered a success if the device is not explanted for safety reasons during the 12-month to 5 year post-implant evaluation. This study is not being proposed to support marketing applications (510(k) or PMA) for the NeuroPort Arrays. Instead, the goal is to demonstrate that three-dimensional microelectrode arrays provide a safe way to record sufficient neural information for controlling complex assistive devices that will increase the independence of individuals with disabilities.

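### The safety success label counts a death with arrays in place, a declined safety explant and an early non-safety removal as successes, and in the extension it has no fixed window

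*Combined protocol and SAP*

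**What the plan says.** One test appears four times in the combined protocol and SAP.

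- Core study, per participant (2.5.1): "A participant will be considered a success for safety if the device is not explanted for safety reasons during the 12-month post-implant evaluation".
- Core study, study level (2.5.3): "The study will be considered a success if the device is not explanted for safety reasons during the 12-month post-implant evaluation". The sentence that follows it asks for control of an assistive device in a daily-living task, which mainly concerns efficacy.
- Extension, per participant (3.5.1): "A participant will be considered a success for safety if the device is not explanted for safety reasons during the 5 year post-implant evaluation". The same subsection opens with "The NeuroPort Arrays will be removed up to 5 years after implantation".
- Extension, study level (3.5.3): "The study will be considered a success if the device is not explanted for safety reasons during the 12-month to 5 year post-implant evaluation".

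The time in the extension is elective. Under 3.3.3, participants may "decide to extend the implantation for any duration between 6 months and 4 years", and "This can be decided at any point during the study". Section 3.4.2 puts removal at "approximately 5 years after implantation of the NeuroPort Arrays", while allowing for earlier removal.

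Safety is also documented outside the success rule. Adverse events are assessed at every stage in Table 1 (2.4.5). They are documented at least weekly for Aim 1a (2.5.3, 3.5.3) and recorded and reported under 4.2. None of that carries a success threshold. Section 2.5.2 makes demonstrating safety part of the main goal, plans single-subject analyses, and caps implants at five.

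**The concern.** The rule defines success by the absence of one action, a removal on safety grounds. It does not ask whether the participant survived, whether a removal was advised and refused, or whether the participant was observed for the whole period. No section states which removals count as made for safety reasons. Sections 2.4.4, 3.4.4 and 4.3 list complications that could lead to removal, but they put technical malfunction in the same list as infection and serious medical complications. The study-level sentences speak of a single device and do not say how up to five participants combine.

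At stake is the meaning of the word success in the report. It could be attached to a participant whose adverse event record shows a device-related death, or to one observed for a quarter of the period. With at most five implants, each participant is at least a fifth of the evidence.

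**Working it through.** The plan gives no target rate, success count, alpha or power for safety, so there is no planned figure to reproduce. The check applies the rule as written to courses that the protocol itself foresees.

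| Course | Where foreseen | Rule read literally | Under the proposed fix |
|---|---|---|---|
| A. Death with arrays in place | 4.1 (Table 2), 4.2.1 | Success: no explant | Failure if associated with device or procedure; otherwise listed separately with its month |
| B. Explant recommended for a treatment-resistant serious event, declined | 4.1 (a recommendation), 2.4.4 (disagreement over explant) | Success: no explant | Failure |
| C. Removal at, say, month 3 for non-compliance | 2.4.2, 2.4.4 | Success: explanted, but not for safety | Incomplete, with month and reason |
| D. Serious device event treated, arrays kept to month 12 | 2.5.1, 4.1 | Success | Success, with the event shown beside it |
| E. Safety explant attempted, array left because of fibrosis | 4.1 (put below 1%) | Success, if leaving the array counts as not explanted | Failure |

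**Tallies (assumed mixes, to test the rule and not to forecast).**

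- Four uneventful completers and one device-associated death. Present rule: 5 successes, 0 failures. Fix: 4 successes, 1 failure.
- One uneventful completer and one each of A (device-associated), B, C and D. Present rule: 5 successes. Fix: 2 successes (one shown with a serious event), 2 failures, 1 incomplete.

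**Chance of course A.** Table 2 in 4.1 rates death as rare, defined as below 1%. With p = 0.01 as the ceiling, n = 5 implants (the maximum in 2.5.2) and independence:

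P(at least one death) = 1 − (1 − 0.01)^5 = 1 − 0.951 = 0.049, so at most about 4.9%.

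Without independence the bound is 5 × 0.01 = 5%, nearly the same. The documents give no rate for B or C.

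**Extension window.** Section 3.3.3 allows 6 months to 4 years beyond the 1-year implantation.

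- Shortest elective course: 12 + 6 = 18 months.
- Longest: 12 + 48 = 60 months.
- Ratio: 60 / 18 = 3.3, so the shortest course is 18 / 60 = 30% of the longest.

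**Core window.** Section 2.5.1 plans removal at 1 year ± 30 days: 365 − 30 = day 335 to 365 + 30 = day 395. A strict 365-day completion rule would wrongly class an on-schedule removal at day 335 as incomplete, so the fix must allow for this.

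**The case against.** The strongest reply is that safety is not judged by this label. Aim 1a is fulfilled by adverse event documentation, no pooled success proportion is planned, and the study is not meant to support a marketing application. This stands, and it limits the point to the label. A reader might infer that deaths or serious events would go unseen. The documents do not support that: 2.4.5, 2.5.3, 3.5.3 and 4.2 provide for their assessment and reporting.

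A second reply concerns course D. Counting an event that resolves with treatment as tolerated is a defensible feasibility endpoint, and 2.5.1 ties early explant to treatment-resistant events. This also stands. A reader might take the infection risk in 4.1 (below 9% for two pedestals) and compute 1 − 0.91^5 = 37.6% as the chance of a mislabelled participant among five. That does not follow. A treated infection with arrays retained keeps the success label under the fix, so the figure measures a label that does not change.

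Third, the passage in 2.4.4 on disagreement over explant does not say that the reason is safety, and 2.5.1 discusses refusal mainly for arrays staying beyond 1 year. That is fair, but 4.1 makes explant for a treatment-resistant serious event a recommendation, so a refusal inside the window remains possible.

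Fourth, mention of a 12-month evaluation may imply completion. It may, but nothing says so. Nor is early non-safety removal simply unclassified, as a reader might infer: on the literal wording it meets the rule.

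Fifth, the extension wordings largely fit one range. Removal at up to 5 years, an evaluation from 12 months to 5 years, and an elective 6 months to 4 years can be read together. A reader might infer a flat contradiction. What remains is mainly the 5-year wording in 3.5.1, and the lack of a stated window behind the label.

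**Conclusion.** The point holds as a defect in the success label. The plan's only safety success criterion, followed exactly, scores courses A, B and C as successes, and the extension label can stand for anything from about 18 to 60 months. Course D also scores as a success; that is acceptable provided the label is never reported without the event.

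The size is modest. At the protocol's own ceiling of 1%, the chance of at least one death in five implants is at most about 4.9%. That assumes all five are implanted and takes Table 2's category as a per-participant risk. No probability can be given from the documents for a declined explant or an early non-safety removal. The literal scoring itself needs no numerical assumption.

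Severity: a minor to moderate labelling fix. Nothing here shows a gap in participant monitoring.

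**What to change.** Amend 2.5.1, 2.5.3, 3.5.1 and 3.5.3.

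1. **Failures.** Score as a safety failure:
   - an explant for any of the safety or medical complications listed in 2.4.4, 3.4.4 and 4.3, without requiring device association. Requiring association could remove from the failures some explants for serious medical complications that count now;
   - an explant advised for such a reason and declined, or attempted with an array left in place;
   - a death associated with the device or procedure.

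   Never score any other death in the window as a success; list it separately with its month. Say whether the psychological distress item in 3.4.4 counts as a safety reason.
2. **Completion.** Score success only for participants observed to the end of the window. In the core study, count planned removal within the ± 30 days (day 335 onward) as complete. List early non-safety removals as incomplete, with month and reason.
3. **Companion count.** Beside the label, report how many participants had a serious adverse effect (4.2.1) associated with the device or procedure, through the 4-week post-explant visit (2.4.3, 3.4.3).
4. **Extension and study level.** State one extension window counted from implant, show months observed per participant, and say how participants combine into the study-level result.

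The sponsor should also reconcile four places on when participation ends or arrays are removed: 2.4.4 (surgical intervention), 4.3 (any intervention), 2.5.1 (arrays are explanted) and 4.1 (explant is recommended). This review does not say which is right.

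Cost: wording in four subsections, and one case report line for the date of, reason for and response to any explant advice. Existing adverse event assessment and follow-up visits supply the rest, and one line per participant is enough. The downside is that the safety result may look less favourable, and some participants will be shown as incomplete.
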